d. If DLT's are observed in 2/6 or more patients, this dose level would exceed the MTD, and the induction chemotherapy dose will be reduced to vosaroxin at a dose of 50 mg/m² IV on days 1 and 4 in the first cycle (induction 1) for a total dose of 100 mg/m²/cycle and the decitabine will be reduced to 20 mg/m² IV for only 4 consecutive days (Days 1 to 4). Six patients will be treated to evaluate the safety of this schedule, and after consultation with and approval of the PI. If DLTs are observed in 0-1/6 in phase I, the study will open broadly for the phase II at this schedule at this dose schedule.

After the first 6 subjects have been treated with vosaroxin and decitabine at the selected MTD (either dose-level a, b, or d), and assessed for toxicity, a summary and rationale to continue enrollment will be provided by the study team to the IND Office including a separate cohort summary for each dose level tested. These will be reviewed by the IND Office Medical Monitor. The IND Office Medical Monitor will indicate whether the study may continue enrollment.

4.5 Induction Therapy in Phase II:

Following the phase I portion to ensure safety, all subsequent patients will receive the following induction regimen (induction 1):

- a. Vosaroxin intravenously on days 1 and 4 at a dose of 70 mg/m² for a total dose of 140 mg/m²/cycle (days 1 and 4), or the final induction dose (MTD) determined in phase I.
- b. Decitabine IV at a dose of 20 mg/m² for 5 consecutive days (days 1 to 5), or the final induction dose (MTD) determined in phase I.

The 70mg/m² day 1 and 4 dosage of vosaroxin has been implemented in the REVEAL-I study (single agent vosaroxin in elderly AML) and was felt to be as efficacious as the 90 mg/m² dose with a lower incidence of mucositis. Based on our current experience and the data from REVEAL 1 we would like to request IND approval to reduce the vosaroxin induction dose from 90 mg/m² days 1 and 4 to 70 mg/m² days 1 and 4 with the intention of decreasing toxicity while maintaining equivalent efficacy.

Treatment may be repeated every 4-7 weeks. If a dose is missed, the patient may take the missed dose if it has been less than 48 hours.

Patients, who have not achieved any response (CR, CRp, Cri) following the initial induction (induction 1) course, can receive one additional induction course (induction 2) at the same dose as induction 1 or other dose modifications for re-induction may be made in the best interest

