If the peripheral count recovery is delayed beyond 42 days from Day 1 of the prior induction or re-induction cycle and the delay is presumed to be secondary to the induction therapy, the study drug doses for the consolidation must be reduced as follows: reduce the dose of vosaroxin to 50 mg/m^2 IV on days 1 and 4 for a total dose of $100 \text{ mg/m}^2/\text{cycle}$ in combination with decitabine at a dose of 20 mg/m^2 intravenously for 5 consecutive days (Days 1 to 5).

Consolidation cycles to be given every 4-8 weeks upon recovery of counts and toxicities. Consolidation cycles may be given beyond the stipulated 8 weeks if approved by the study PI.

If the patient experienced a dose modification during induction, the patient may remain at the modified dose level or return to the original dosing schedule during consolidation as determined to be in the patient's best interest by the treating physician and PI. Dose adjustments to the subsequent cycles of the consolidation schedule will depend on toxicity with previous courses. Dose adjustments felt to be in the best interest of the patient are allowed but must be discussed with PI and the discussion documented in the patient's medical record. For clinically significant, study regimen related grade 3-4 toxicities, reduce the dose of vosaroxin to 50 mg/m² *Non* days 1 and 4 for a total dose of 100 mg/m²/cycle in combination with decitabine at a dose of 20 mg/m² intravenously for 5 consecutive days (Days 1 to 5). If Grade 3 or 4 toxicities recur or persist at this lower dose, reduce the dose of vosaroxin to 50 mg/m² IV on days 1 and 4 for a total dose of 100 mg/m²/cycle in combination with decitabine at a dose of 20 mg/m² intravenously for 4 consecutive days (Days 1 to 4). If Grade 3 or 4 toxicities recur or persist at this lower dose, reduce the dose of vosaroxin to 50 mg/m² IV on days 1 and 4 for a total dose of 100 mg/m²/cycle and reduce the decitabine to 20 mg/m² *N* for only 3 consecutive days (Days 1 to 3)

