Other dose modifications may be permitted if in the patient's best interest after discussion with the Principal Investigator and the discussion documented in the patient's medical record. Vosaroxin may be omitted in consolidation cycles for patients in CR/Cri/CRp based on their toxicity in the first cycle, as judged by the treating physician, and only after discussion with the PI. Up to a total of 7 cycles of induction-consolidation will be given (up to 2 induction cycles and up to 5 consolidation cycles).

4.7 Management of Toxicities and Dose Modifications:

4.7.1 Induction, Re-Induction, and Consolidation Cycles:

All dose delays, reductions, and modifications for hematologic and non-hematologic toxicities will be assessed according to sections 4.7.2 and 4.7.3.

4.7.2 Hematologic (Blood/Bone marrow) Toxicity:

No dose reductions, delays, or modifications are required for hematologic toxicities during the induction or re-induction cycles. It is assumed that low counts at diagnosis are due to involvement by the disease process and require therapy for improvement. Likewise, patients who are considered for re-induction have persistent disease and thus no recovery of hematologic parameters can be expected. Patients who achieve a CRJCRp/CRi should receive the consolidation cycle no sooner than 28 days from Day 1 of the previous induction or re-induction cycle, provided their peripheral blood counts have recovered (ANC $\geq 1.0 \times 10^9/L$ and platelet count $\geq 50 \times 10^9/L$). If patient has documented CR they may proceed with consolidation cycles even if the platelet count remains $\leq 50 \times 10^9/L$ if approved by the PI. If patient has documented CRi they may proceed with consolidation cycles even if the platelet count remains $\leq 50 \times 10^9/L$ and/or ANC $\leq 1.0 \times 10^9/L$ if approved by the PI. If the peripheral count recovery is delayed beyond 42 days from Day 1 of the prior induction or re-induction cycle and

the delay is presumed to be secondary to the induction therapy, the study drug doses for the consolidation must be reduced as follows: reduce the dose of vosaroxin by one dose level as described in section 4.7.4 in combination with decitabine at a dose of 20 mg/m^2 intravenously for 5 consecutive days (Days 1 to 5).

4.7.3 Non-hematologic Toxicity:

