If persistent grade 2 toxicity occurs after completion of a cycle of therapy (i.e., after day 5 of an induction treatment cycle or day 5 of a consolidation treatment cycle), and it is unresponsive to optimal treatment and is thought to be possibly related to vosaroxin treatment, vosaroxin treatment may be delayed up to 21 days after the onset of an event or until the AE has returned to baseline or \leq grade 1. Then administer 100% of the planned dose. If toxicity persists longer than 21 days or recurs, the vosaroxin dose may be delayed and the dose of vosaroxin will be reduced as specified in section 4.7.4. Additional dose reductions can be performed, as specified in section 4.7.4, if toxicity recurs or persists during induction or consolidation treatment cycles respectively. If the toxicity recurs or persists after reducing to the lowest level as outlined in section 4.7.4, then further dose reductions will not be permitted and the patient will be taken off study unless otherwise discussed with the PI.

If grade 2:3 toxicity occurs after completion of the vosaroxin treatment (i.e., after day 5 of an induction treatment cycle or day 5 of a maintenance treatment cycle), and it is suspected that vosaroxin played a role in toxicity, the next scheduled cycle of vosaroxin therapy should be withheld until toxicity returns to grade 0 or 1 or to baseline. The dose of vosaroxin for each subsequent cycle will be reduced as specified in section 4.7.4. Additional dose reductions can be performed, as specified in section 4.7.4, if the toxicity recurs or persists. If the toxicity recurs or persists after reducing to the lowest dose level, then further dose reductions will not be permitted and the patient will be taken off study unless otherwise discussed with the PI.

For those patients who are receiving consolidation cycles of Decitabine with no Vosaroxin, as discussed in section 4.6, dose adjustments will be allowed based on the discretion of the treating physician. The Dose adjustments for the Decitabine will follow the same dose adjustments listed in section 4.7.4.

Dose modifications different from those stated in the protocol will be evaluated by the principal investigator and the sponsor -MDACC IND office and may only be allowed after approval by PI.

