4.7.4 Dose Modifications

Dose Modifications

Dose Level	Vosaroxin	Decitabine
	D1 & D4	
-3	50 mg/m ²	20 mg/m ² (Days 1 - 3)
-2	50 mg/m ²	20 mg/m ² (Days 1 -4)

-1	50 mg/m ²	20 mg/m ² (Days 1-5)
0	70mg/m ²	20 mg/m ² (Days 1-5)

4.7.5 Supportive Care:

Supportive care measures including blood products, infection prophylaxis and growth factors will be administered according to institutional and Leukemia Department guidelines.

4.7.6 Concomitant Medications:

Concomitant medications are recommended as prophylaxis for nausea, vomiting, and infections, and are allowed for managing myelosuppression as shown in Table 6. Myelosuppression is expected in patients with AML due to underlying disease, as well as due to chemotherapy (such as vosaroxin and decitabine), or both. Most patients have neutropenia, thrombocytopenia, or both at study entry. Myelosuppression may be managed with growth factor support and blood transfusion according to institutional standard of care, American Society of Clinical Oncology (ASCO) Practice Guidelines, and NCCN Practice Guidelines.

Infections secondary to myelosuppression are common in patients with AML, and may be related to underlying disease, chemotherapy, or both. Therefore, the use of prophylactic antibiotics, antifungal agents, and antiviral agents is recommended. A suggested regimen is ciprofloxacin (500 mg po q 12h), fluconazole (200 mg po qd), and acyclovir (800 mg po q 12h). One dose of prophylactic intrathecal chemotherapy will be allowed with diagnostic lumbar puncture.

All ongoing medications and therapies (including herbal products, nutritional supplements, and nontraditional medications) at screening will be considered prior medications. Concomitant medication data will not be collected or entered into the case report form; however, the subject's medication record will contain a list of concomitant medications. Patients will discontinue study treatment if they intentionally receive or require treatment with a medication prohibited by the protocol. If however prohibited medication is inadvertently administered/ taken by the patient, the patient may remain on study as long as the prohibited medication is discontinued as soon as feasible. End-of-treatment procedures will be performed, and follow-up will commence. Prohibited medications are shown in Table 6.

Table 6: Instructions for the use of concomitant medications and therapies

Category of Use	Medication	Comment on Use	Restriction on Use

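### The mandatory consolidation cut for late count recovery (4.6, 4.7.2) gives no reduction to a patient whose last cycle was already at vosaroxin 50 mg/m² with decitabine Days 1-5

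*Combined protocol and SAP*

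**What the plan says.** The trigger in section 4.6 is: "If the peripheral count recovery is delayed beyond 42 days from Day 1 of the prior induction or re-induction cycle". The delay must also be presumed to come from the induction therapy. The instruction is then that "the study drug doses for the consolidation must be reduced as follows: reduce the dose of vosaroxin to 50" mg/m² (100 mg/m² per cycle), with decitabine 20 mg/m² on Days 1-5.

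Section 4.7.2 repeats the rule in other words: "reduce the dose of vosaroxin by one dose level as described in section 4.7.4 in combination with decitabine at a dose of 20" mg/m², again on Days 1-5.

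Table 4.7.4 has four rows: 70 mg/m² with Days 1-5 (level 0), 50 with Days 1-5 (level -1), 50 with Days 1-4 (level -2) and 50 with Days 1-3 (level -3). Vosaroxin is the same in all three reduced rows.

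Two provisions can put a Phase II patient at 50 mg/m² before consolidation:

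- Section 4.7.3 covers grade 3 or higher toxicity after a cycle in which vosaroxin is suspected: "The dose of vosaroxin for each subsequent cycle will be reduced as specified in section 4.7.4".
- Section 4.5 allows induction 2 to be given "at the same dose as induction 1 or other dose modifications for re-induction may be made in the best interest" of the patient, after discussion with the PI.

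Section 4.4 also allows induction at 50 mg/m² with Days 1-5 (Phase I level c) or Days 1-4 (level d).

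**The concern.** The rule is a mandatory safety reduction for prolonged myelosuppression attributed to treatment. It names a destination, not a step. That is adequate while every patient arrives from a higher dose. It fails for a patient who already needed a lower dose, was re-induced at it, responded, and then recovered late. That patient meets the trigger, yet the required dose is the one that preceded the delay.

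Section 4.7.2 looks as if it should solve this, because it speaks of a dose level. It does not: the only steps left in 4.7.4 remove decitabine days, and 4.7.2 holds decitabine at five days.

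At stake is whether a patient with demonstrated intolerance gets any reduction by default, or only if someone notices and asks for an exception.

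**Working it through.** **Inputs.** Vosaroxin is given twice per cycle, so the cycle dose is 2 × the daily dose. Decitabine is 20 mg/m² per day, so the cycle dose is 20 × the number of days.

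**The plan's own figure.** 2 × 50 = 100 mg/m² of vosaroxin per cycle, as stated in 4.6. Likewise 2 × 70 = 140 and 2 × 90 = 180. Decitabine is 20 × 5 = 100, 20 × 4 = 80 and 20 × 3 = 60 mg/m² per cycle.

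**The 4.6 target against the dose last given.** Change = target ÷ last dose − 1, with a target of 100 mg/m² for each drug.

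| Last cycle | Vosaroxin per cycle | Decitabine per cycle |
|---|---|---|
| 90, Days 1-5 | 180 to 100: 100/180 − 1 = −44.4% | 100 to 100: 0% |
| 70, Days 1-5 | 140 to 100: 100/140 − 1 = −28.6% | 100 to 100: 0% |
| 50, Days 1-5 | 100 to 100: 0% | 100 to 100: 0% |
| 50, Days 1-4 | 100 to 100: 0% | 80 to 100: 100/80 − 1 = +25% on a literal reading |

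**The 4.7.2 wording.** One level down from level -1 is level -2, where vosaroxin is still 50 mg/m². With decitabine held at Days 1-5, the dose is again 50 with Days 1-5, a 0% change. From level -2 the result is also as in the table.

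**Whether a Phase II patient can be there.** Induction 1 is at 70 with Days 1-5. Grade 3 or higher toxicity follows, with vosaroxin suspected, and there is no response. Section 4.7.3 then requires one level down, so induction 2 is at 50 with Days 1-5. The late-recovery trigger expressly covers re-induction. If the patient responds but recovers after day 42, the mandatory reduction is 0%. This route needs no discretionary dose decision.

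**With a one-row step from the dose last given.** From 50 with Days 1-5 to Days 1-4: 80/100 − 1 = −20% decitabine. From Days 1-4 to Days 1-3: 60/80 − 1 = −25%.

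**The case against.** **The comparator.** The rule governs consolidation doses, and the default consolidation dose in 4.6 is 70 mg/m² with Days 1-5. A patient modified in induction may go back to the original schedule. Against that default the rule cuts vosaroxin from 140 to 100 mg/m² (−28.6%) and removes the option of returning to 70. This stands, so it would be wrong to say that the rule does nothing. But the delay followed the dose last given, and from that dose there is no reduction.

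**Discretion.** Section 4.6 lets a patient stay at a modified dose, permits other adjustments after discussion with the PI, and in some cases allows vosaroxin to be omitted. These provisions can protect an individual patient. They are permissive, and they leave the mandatory rule uncorrected.

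**More decitabine.** A reader might infer that the protocol orders 25% more decitabine after late recovery. The literal text gives that result from Days 1-4, but it contradicts the rule's own instruction to reduce, and 4.6 expressly lets the patient remain at the modified dose. The case also depends on the lower Phase I levels having been used, or on a dose agreed individually with the PI. The documents do not report the Phase I result. However, the request in 4.5 to move induction from 90 to 70 mg/m² suggests that level d was probably never opened.

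**The grade 3-4 toxicity rule.** A reader might see the same defect in 4.6 where it says "For clinically significant, study regimen related grade 3-4 toxicities, reduce the dose of vosaroxin to 50" mg/m². Its first step does have a fixed target, but the next steps, for toxicity that recurs or persists, go to Days 1-4 and then Days 1-3. That ladder largely repairs itself. It does not clearly repair the late-recovery rule, which makes no reference to it, and 4.7.1 sends hematologic toxicity to 4.7.2.

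**The Phase I MTD.** A reader might also think that 4.5 and 4.6 need an added cap at the Phase I MTD. Section 4.4 already carries the level cleared in Phase I forward to all later patients, so no such wording is needed.

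**Conclusion.** The point holds in a narrow form. As written, 4.6 and 4.7.2 give a 0% reduction from the dose last given, in both drugs, to a patient whose prior cycle was at vosaroxin 50 mg/m² with decitabine Days 1-5. For that patient the rule only prevents a return to 70 mg/m². For patients coming from 90 or 70 mg/m² it works as intended.

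The 0% takes the last induction or re-induction dose as the comparator and assumes that no discretionary change is made. The documents give no rates of re-induction, toxicity reduction or late recovery, so the number of patients cannot be estimated. The required sequence of events suggests few.

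The primary analysis is untouched: response is assessed after the induction cycles (10.2), and the toxicity stopping boundaries use first-cycle events (10.3). Severity is low. This is a defect in a safety instruction and does not threaten the trial's conclusions.

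**What to change.** In 4.6 and 4.7.2:

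- Keep vosaroxin 50 mg/m² with decitabine Days 1-5 as the target for patients whose prior cycle was at 90 or 70 mg/m².
- For patients already at 50 mg/m², move one row down Table 4.7.4 from the dose last given: Days 1-5 to Days 1-4, or Days 1-4 to Days 1-3.
- At Days 1-3 no row remains, so the PI decides.

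Matching wording in the first step of the 4.6 grade 3-4 rule is optional, since its later steps already use the lower rows.

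The cost is one sentence in each of two sections of a protocol amendment. It needs no new dose level, no extra patients and no change to the analysis.

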If clinically significant grade 2 toxicity occurs during a course of induction or consolidation therapy, and it is unresponsive to optimal treatment and is thought to be possibly related to vosaroxin treatment, vosaroxin treatment may be withheld after the onset of an event until the adverse event (AE) has returned to baseline or \leq grade 1. If the AE has returned to baseline or \leq grade 1 within the 5-day induction or 5-day consolidation treatment interval from the start of therapy, treatment may resume at the same dose, but missed doses will not be made up. If the AE has returned to \leq grade 1 before administration of the next cycle, no dose reductions will be made with subsequent cycles.

If grade 3 or greater toxicity occurs during a course of induction or consolidation therapy, and it is unresponsive to optimal treatment and is thought to be possibly related to vosaroxin treatment, vosaroxin treatment may be withheld after the onset of an event until the AE has returned to baseline or \leq grade 1. If the AE has returned to baseline or \leq grade 1 within the 5-day induction or 5-day consolidation treatment interval from the start of therapy, treatment may resume but at a reduced dose. Reduce the dose of vosaroxin by one dose level as described in section 4.7.4 for the day 4 dosage of that cycle only. Missed doses will not be made up. In subsequent cycles of therapy, the dose of vosaroxin will remain at the reduced dose level for each subsequent cycle in combination with decitabine at a dose of 20 mg/m^2 intravenously for 5 consecutive days (Days 1 to 5). If the toxicity recurs or persists in spite of reducing the vosaroxin dose to, further dose reductions as outlined in section 4.7.4 will be allowed. If the toxicity recurs or persists after reducing to the lowest dose level, as described in section 4.7.4, then no further dose reductions will be permitted and the patient will be taken off study unless otherwise discussed with the PI.

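### Sections 4.6 and 4.7.3 set different triggers for reducing vosaroxin in consolidation, and the protocol does not settle which one governs

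*Combined protocol and SAP*

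**What the plan says.** Section numbers below are those printed in the body of the protocol, not the contents list.

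- **4.6 (post-remission therapy).** "For clinically significant, study regimen related grade 3-4 toxicities, reduce the dose of vosaroxin to 50" mg/m² on days 1 and 4, with decitabine unchanged at the first step. The event must be clinically significant and related to the regimen. The sentence does not ask which of the two drugs is responsible, whether the event responded to treatment, or whether it is hematologic. 4.6 also allows departures: "Dose adjustments felt to be in the best interest of the patient are allowed but must be discussed with PI".
- **4.7.1 (induction, re-induction and consolidation).** "All dose delays, reductions, and modifications for hematologic and non-hematologic toxicities will be assessed according to sections 4.7.2 and 4.7.3". Section 4.6 is not named.
- **4.7.2 (hematologic).** "No dose reductions, delays, or modifications are required for hematologic toxicities during the induction or re-induction cycles". Before consolidation, a reduction follows "If the peripheral count recovery is delayed beyond 42 days from Day 1 of the prior induction or re-induction cycle" if the delay is presumed due to induction. Section 4.6 carries the same 42-day rule.
- **4.7.3 (non-hematologic), during the course.** The rule opens: "If grade 3 or greater toxicity occurs during a course of induction or consolidation therapy, and it is unresponsive to optimal treatment". It adds that the event must be thought possibly attributable to vosaroxin.
- **4.7.3, after day 5.** A grade 3 or greater event leads to a reduction in later cycles if it occurs then "and it is suspected that vosaroxin played a role in toxicity". Response to treatment is not a condition here.

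**The concern.** Both sections apply to a patient in consolidation, and both are written as the default rule. They turn on different facts: 4.6 on relation to the regimen, 4.7.3 on a vosaroxin role and, during the course, on failure to respond to treatment. Two investigators could each follow the protocol faithfully and give the same patient different vosaroxin doses.

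Consolidation runs to as many as five cycles. Safety, toxicity, disease-free survival and duration of response are secondary objectives in Section 1.2.2, and all are observed under whatever dose is given there. Section 7.3 lists noncompliance with dose, including reductions, as a class of violation or deviation. In the cases where the sections differ, that classification has no single standard to apply.

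**Working it through.** The protocol states no figure on this point. The check sets the rules side by side for defined cases and then sizes the dose difference per patient.

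**Step 1: do the ladders differ?** No. The three steps in 4.6 are vosaroxin 50 mg/m² with decitabine for 5, then 4, then 3 days. These are levels -1, -2 and -3 of the table in 4.7.4. The disagreement is confined to the trigger.

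**Step 2: cases in consolidation.**

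| Case | 4.6 | 4.7.2 / 4.7.3 |
|---|---|---|
| A. Clinically significant grade 3-4 non-hematologic event after day 5, vosaroxin suspected | reduces | reduces |
| B. Clinically significant, regimen-related grade 3-4 event on days 1-5 that responds to treatment | reduces | no trigger met |
| C. Clinically significant, regimen-related grade 3-4 event attributed to decitabine only, any day of onset | reduces vosaroxin | no trigger met |
| D. Grade 3-4 cytopenia with counts recovered by day 42 | not stated whether covered | no trigger met |
| E. Grade 2 event lasting beyond 21 days or recurring, possibly vosaroxin-related | no trigger stated | reduces |

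Case B fails the during-course rule because the event responded, and the other grade 3 rule is for onset after day 5. Case C fails both grade 3 rules because each needs a possible or suspected vosaroxin role. Cases B and C are the firm conflicts. Case D depends on the scope of the 4.6 sentence, which the text leaves open. In case E, 4.7.3 is the wider of the two.

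For grade 4 events there is a further overlap. Section 7.2.3 lists clinically significant grade 4 drug-related non-hematologic toxicity as a reason for required discontinuation, so B and C are cleanest for grade 3.

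**Step 3: dose difference where the readings part.** Inputs: 70 mg/m² on days 1 and 4 (4.6, and level 0 of 4.7.4); 50 mg/m² on days 1 and 4 (levels -1 to -3); up to five consolidation cycles.

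- Per affected cycle: 2 × 70 = 140 against 2 × 50 = 100 mg/m². (140 − 100)/140 = 29%.
- Event first arising in consolidation cycle 1, all five cycles given: 4.6 adjusts subsequent cycles, so at most four differ. 5 × 140 = 700 against 140 + 4 × 100 = 540 mg/m². (700 − 540)/700 = 23%.

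Lower ladder steps shorten decitabine only, so they do not change these vosaroxin totals.

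**The case against.** The best defence is that 4.7.1 already names the governing sections, that the principal investigator may approve departures under either section, and that the primary endpoint is untouched.

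- **4.7.1 governs.** It points to 4.7.2 and 4.7.3, but 4.6 keeps its own directive for the same cycles and nothing withdraws it.
- **Discretion.** Permission to depart from a default does not say what the default is. The routes also differ: 4.6 asks for discussion with the principal investigator and documentation, while 4.7.3 asks for evaluation by the principal investigator and the IND office, with the principal investigator's approval.
- **Primary endpoint.** This stands. Response is evaluated after the first and second induction cycles (10.2), before consolidation.

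A reader might also infer stronger versions, which the documents do not support.

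- *4.7 is much narrower throughout.* It is not. After day 5 a suspected vosaroxin role is enough and clinical significance is not required, so 4.7.3 is about as wide as 4.6 there. It is wider for persistent grade 2 events.
- *The same patient is ordered to be both reduced and kept at full dose.* For a grade 3 event that responds to treatment, 4.7.3 is silent. It gives no order to hold full dose.
- *The hematologic rules conflict.* Both sections carry the same 42-day rule, and 4.6 speaks of recovery of counts and of toxicities as separate things. That favors reading its grade 3-4 sentence as non-hematologic, although it does not say so.
- *Table 5 sizes the gap*, for example 43% (febrile neutropenia) or 27% (sepsis/bacteremia) reduced under 4.6 against about 0% under 4.7. Table 5 gives neither day of onset nor attribution, and events like case A are reduced under both sections. It also describes relapsed or refractory patients given vosaroxin 80 to 90 mg/m² with cytarabine.
- *700 against 500 mg/m² over five cycles.* That needs a reduction from the first consolidation cycle, which an event arising in consolidation cannot cause. A dose already modified in induction falls under 4.6's discretionary clause on staying at or returning from the modified dose.

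**Conclusion.** The conflict is real but limited. Sections 4.6 and 4.7.3 give different answers in at least two cases: a grade 3-4 event on days 1-5 that responds to treatment, and a regimen-related event attributed only to decitabine, whatever its day of onset. They agree for clinically significant non-hematologic grade 3-4 events after day 5 with vosaroxin suspected. Whether 4.6 also covers cytopenias is an open question of scope.

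The share of patients affected cannot be derived from the documents and could be small. For an affected patient the difference is 29% of the vosaroxin dose per cycle, and at most 23% of the five-cycle total when the event first arises in consolidation cycle 1. These figures assume consolidation at the 70 mg/m² level, all five cycles given, and no discretionary change. The matter bears on patient safety in consolidation, on the secondary endpoints and on judging dose compliance. It should be corrected.

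**What to change.** Reconcile 4.6 with 4.7.1 to 4.7.3. State the trigger for a vosaroxin reduction once, and make that statement explicit on four points:

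- attribution: to the regimen, or to vosaroxin in particular;
- whether hematologic events are included;
- whether response to treatment matters;
- whether the rule changes with day of onset.

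Replace the ladder text in 4.6 with a cross-reference to that statement and to 4.7.4. In the same edit, align the review route for departures and check the wording for grade 4 events against 7.2.3. Which trigger applies is for the sponsor and the investigator to decide.

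The cost is a protocol wording amendment, with no extra patients or assessments.
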